## 825 **7.6 Rescue Medications, Treatments, and Procedures**

- All participants will be required to have a commercially available standard care glucagon (or glucagon
- analog) preparation for treatment as needed of severe hypoglycemia.

## 828 **7.7 Participant Compensation**

829 Participant compensation will be specified in the informed consent form.

#### 830 **7.8 Participant Withdrawal**

Participation in the study is voluntary, and a participant may withdraw at any time. For participants who withdraw, their data will be used up until the time of withdrawal.

#### **7.9 Confidentiality**

- 834 For security and confidentiality purposes, participants will be assigned an identifier that will be used
- instead of their name. Protected health information gathered for this study will be shared with the
- 836 coordinating center, the Jaeb Center for Health Research in Tampa, FL. De-identified participant
- information may also be provided to research sites involved in the study.

# 838 Chapter 8: Statistical Considerations

## 839 8.1 Statistical and Analytical Plans

The approach to statistical analysis is summarized below. A detailed statistical analysis plan (SAP) will be written and finalized prior to the start of the study.

#### 842 **8.2 Statistical Hypotheses**

- The primary outcomes for this study are safety outcomes: hypoglycemia and hyperglycemia measured by adverse events and CGM. Statistical hypotheses are stated for the CGM-measured outcomes only.
- CGM-measured percentage below 54 mg/dL and CGM-measured percentage above 250 mg/dL will be tested for non-inferiority over an 8-week period.
- 847 The null/alternative hypotheses are:
- 848 Percentage below 54 mg/dL:
- a. *Null Hypothesis*: The difference in mean CGM-measured % below 54 mg/dL between the 8
   weeks follow-up and baseline is greater than or equal to +0.5% (non-inferiority).
- b. *Alternative Hypothesis*: The difference in mean CGM-measured % below 54 mg/dL between the
  8 weeks follow-up and baseline is less than +0.5%.

#### 853 Percentage above 250 mg/dL:

- a. *Null Hypothesis*: The difference in mean CGM-measured % above 250 mg/dL between the 8 weeks follow-up and baseline is greater than or equal to +3% (non-inferiority).
  b. *Alternative Hypothesis*: The difference in mean CGM-measured % above 250 mg/dL between the
- 857 8 weeks follow-up and baseline is less than +3%.
- 858 **8.3 Sample Size**

The study has not been formally powered to test any a priori hypothesis. The goal is to have at least 30 participants complete the 8-week trial period. Some outcomes will be compared between these participants and a sample of participants from the prior PEDAP study.

- 862 **8.4 Endpoints**
- 863

867

868

873

# 8.4.1 Safety Endpoints

- Severe Hypoglycemia (SH) events and SH event rate per 100 person-years
- Diabetic ketoacidosis (DKA) events and DKA event rate per 100 person-years
- Reportable hyperglycemia adverse events with or without ketosis
  - Events related to the study device
    - Events not related to the study device
- Reportable hypoglycemia adverse events that are not severe
- Number of calendar days with any ketone level  $\geq 1.0 \text{ mmol/L}$
- 871 *Hierarchical Safety Endpoints*
- CGM-Measured
  - % Time >250 mg/dL (non-inferiority)

| 874 | 
 
% Time <54 mg/dL (non-inferiority)
 
                                  |  |  |
|-----|--|--|--|
| 875 | Additional Safety Endpoints  |  |  |
| 876 | Other serious adverse events   |  |  |
| 877 | • Any adverse event rate per 100 person-years  |  |  |
| 878 | • Adverse device effects (ADE)   |  |  |
| 879 | • Serious adverse device events (SADE)   |  |  |
| 880 | • Unanticipated adverse device effects (UADE)  |  |  |
| 881 | 8.4.2 Efficacy Endpoints   |  |  |
| 882 | Hierarchical Efficacy Endpoints (tested for superiority compared with baseline)            |  |  |
| 883 | • CGM-Measured   |  |  |
| 884 | 
 
% Time in range 70–180 mg/dL
 
   |  |  |
| 885 | • Mean glucose   |  |  |
| 886 | • % Time >250 mg/dL  |  |  |
| 887 | • % Time <70 mg/dL   |  |  |
| 888 | $\circ$ % Time <54 mg/dL   |  |  |
| 889 | Secondary Endpoints  |  |  |
| 890 | • CGM-Measured   |  |  |
| 891 | 
 
% Time in range 70–140 mg/dL
 
   |  |  |
| 892 | • % Time >180 mg/dL  |  |  |
| 893 | • % Time >300 mg/dL  |  |  |
| 894 | $\circ$ % Time <60 mg/dL   |  |  |
| 895 | 
 
Glucose standard deviation
 
   |  |  |
| 896 | 
 
Glucose coefficient of variation
 
                                       |  |  |
| 897 | 
 
High blood glucose index (HBGI)
 
  |  |  |
| 898 | 
 
Low blood glucose index (LBGI)
 
   |  |  |
| 899 | • Weekly hyperglycemic event rate  |  |  |
| 900 | 
 
Weekly hypoglycemic event rate
 
   |  |  |
| 901 | o Binary   |  |  |
| 902 | 
 
% Time in range 70–180 mg/dL improvement from baseline to 8 weeks ≥5%
 
  |  |  |
| 903 | 
 
% Time in range 70–180 mg/dL improvement from baseline to 8 weeks ≥10%
 
 |  |  |
| 904 | 
 
% Time in range 70–180 mg/dL >70% and % time <70 mg/dL <4%
 
    |  |  |
| 905 | • Insulin  |  |  |
| 906 | • Total daily insulin (units/kg)   |  |  |
| 907 | • Percentage of total insulin delivered via basal  |  |  |

#### 908 Exploratory Endpoints

| 909               | • Insulin   |  |  |
|-------------------|---|--|--|
| 910               | 0   | Total daily basal insulin (units/kg)   |  |
| 911               | 0   | Total daily bolus insulin (units/kg)   |  |
| 912               | 0   | Total daily manual bolus (units/kg)  |  |
| 913               | 0   | Total daily automated bolus (units/kg)   |  |
| 914               | 0   | Number of manual insulin doses per day   |  |
| 915               | 0   | Number of manual insulin doses with carb announcement per day                            |  |
| 916               | 0   | Average daily profile basal rate divided by total daily insulin in percentage points     |  |
| 917               | 0   | Average carbohydrate ratio daily profile (C:I) multiplied by total daily insulin         |  |
| 918               | 0   | Average insulin sensitivity factor daily profile (G:I) multiplied by total daily insulin |  |
| 919               |   | 8.5 Analysis Datasets and Sensitivity Analyses   |  |
| 920
921
922 | To be included in included in analyses of CGM and insulin outcomes, participants must provide at least 168 hours of CGM data for each of the baseline and trial phase and spend at least 50% of the study period in closed-loop mode. |  |  |

923 All participants who enroll in the PEDAP-AI study will be included in the safety analyses of endpoints

that are not measured by CGM. Analyses will include all events that occur between enrollment and the 3-924

Day Post-Study Safety contact or the end of the 71st day after the date of the Closed Loop Initiation 925

visit—whichever is earlier. For participants who do not complete the study, the date of the final contact 926 927

will be used in place of the 3-Day Post-Study Safety contact date.

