# 6.6.1 Participant Discontinuation of Study Device

In the case of an unanticipated system malfunction resulting in a severe hypoglycemia or DKA event (or a

- malfunction that could have led to severe hypoglycemia or DKA), use of the study device will be
- suspended while the problem is diagnosed. The UADE will be reported to the IRB, DSMB, and FDA.
- After assessment of the problem and any correction, use of the study device will not be restarted until approval is received from the IPP DSMP and EDA
- approval is received from the IRB, DSMB, and FDA.
- In the absence of a device malfunction, use of the study device by a participant will be discontinued if any
   of the following occur and the participant will be withdrawn from the study:
- The investigator believes it is unsafe for the participant to continue on the intervention. *This could be due to the development of a new medical condition or worsening of an existing condition; or participant behavior contrary to the indications for use of the device that imposes on the participant's safety*

- The participant requests that the treatment be stopped
- Two distinct episodes of DKA as defined in section 6.2.4
- Two distinct severe hypoglycemia events as defined in section 6.2.3
- One episode of DKA as defined in section 6.2.4 and one severe hypoglycemia event as defined in section 6.2.3

Each DKA or severe hypoglycemia event will be reviewed by the Medical Monitor and by the DSMB

with respect to determination of cause and whether the occurrence of the event can be attributed to use of the study device.

An additional requirement for continued study device use following a single DKA or severe

780 hypoglycemia event will be that the site investigator believes that the event is unlikely to recur and that it

is safe for the participant to continue to use the system. Additionally, if either the Medical Monitor or

- DSMB determines that the occurrence of the event indicates that it is not safe for the participant to
- continue to use the study device, use will be discontinued.

786

Even if the study device system is discontinued, the participant will be encouraged to remain in the study through the final study visit.

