#### 928 **8.6 CGM Metrics Calculations**

929 Baseline values for each CGM metric will be computed from the most recent 28 days of CGM data before 930 the Screening visit.

During the 8-week treatment period, CGM metrics will be calculated from the beginning of study pump 931 use until the end of the day before the final visit. 932

933

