45	o % Timein range70-180 mg/dL					
46	o Mean glucose					
47	o % Time $> 250 \text{ mg/dL}$					
48	o % Time <70 mg/dL					
49	o % Time<54 mg/dL					
50	Secondary Endpoints					
51	• CGM-Measured					
52	o % Time in range 70-140 mg/dL					
53	o % Time>180 mg/dL					
54	o % Time>300 mg/dL					
55	o % Time < 60 mg/dL					
56	o Glucose standard deviation					
57	o Glucose coefficient of variation					
58	o High bloodglucose index (HBGI)					
59	o Low blood glucoseindex (LBGI)					
60	o Weekly hyperglycemiceventrate					
61	o Weekly hypoglycemiceventrate					
62	o Binary					
63	• % Time in range 70-180 mg/dL improvement from baseline to 8 weeks:::5%					
64	• % Time in range 70-180 mg/dL improvement from baseline to 8 weeks:::10%					
65	• % Time in range 70-180 mg/dL $\!>\!70\%$ and % time $\!<\!70$ mg/dL $\!<\!\!4\%$					
66	• Insulin					
67	o Total daily insulin (units/kg)					
68	o Percentage of total insulin delivered via basal					

JAEBCENTERFORHEALTHRESEARCH

69 Exploratory Endpoints

70	•	Insulin	
71		0	Total daily basal insulin (units/kg)
72		0	Total daily bolus insulin (units/kg)
73		0	Total dailymanual bolus (units/kg)
74		0	Total daily automated bolus(units/kg)
75		0	Number of manual insulin doses per day
76		0	Number of manual insulin doses with carb announcement per day
77		0	Average daily profilebasal rate divided by total daily insulin in percentage points
78		0	Average carbohydrate ratio daily profile (C:I) multiplied by total daily insulin
79		0	Average insulin sensitivity factor daily profile (G:I) multiplied by total daily insulin

80 5.3 Analysis Datasets and Sensitivity Analyses

81 To be included in included in analyses of CGM and insulin outcomes, participantsmust provide at least

82 168 hoursofCGMdata for each of the baseline and trial phase and spend at least 50% of the study period83 in closed-loop mode.

84 All participants who enroll in the PEDAP-AI study will be included in the safety analyses of endpoints

85 that are not measured by CGM. Analyses will include all events that occur between enrollment and the 3-

86 Day Post-Study Safety contact or the end of the 71_{st} day after the date of the Closed Loop Initiation

87 visit- whicheveris earlier. For participants who do not complete thestudy, the date of the final contact

88 will be used in place of the 3-Day Post-Study Safety contact date.

89 5.4 CGM Mehics Calculations

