- 200 the second 4-weekperiod will be the end of the day before the 8-Week visit dateor the end of the 59th day
- after the date of the Closed Loop Initiation visit- which ever is earlier. This date will also serve as the end
- 202 of the sixth adaptation period, which will begin at the 6-Week visit. The other five adaptation periods will 203 include data from the adjustment of pump settings at the visit until the adjustment of pump settings at the
- subsequent visit. If the subsequent visit is missed or out-of-window, the end of the period will be the end
- of the day on the latest date that would be in-window for the visit. If a participant misses a vi, sit they will
- 206 be absent from the period begun by that visit. Participants must provide CGM data for at least 75% of the
- 207 time period to be included in the plots and tabulations for that time period.
- 208 7 Safe ty Analyses
- 209 Hierarchical safety endpoints will be analyzed according to the directions in 6.1. All safety endpoints
- 210 listed in 5.1 will be summarized in tables. Details of each reportable adverse event will be provided in a
- 211 listing.

212 8 Intervention Adherence

- 213 The following will be tabulated for the 8-weekstudy period to assess intervention adherence:
- PercenttimeofCGMsensoruse
- Percent time of closed-loop system use
- Percent time in different operational modes
- Percent of Al recommendations that are accepted without any study physician adjustments
- 218
- o For Al recommendations that are adjusted, tabulation of initial and adjusted values

219 System use metrics will be calculated from the beginning of study pump useuntil the end of the day

before the 8-Week visit date or the end of the 59th day after the date of the Closed Loop Initiation visit-

whichever is earlier. For participants who do not complete the study these metrics will be prorated: the

date of the final contact will be used in place of the 8-Week visit date.

223 9 Protocol Adherence and Retention

- 224 The following tabulations and analyses **will** be performed to assess protocol adherence for the study:
- Number of protocol and procedural deviations
- Flowchart accounting for all enrolled participants
- Flowchart of all participants at all scheduled visits and phone contacts after treatment initiation
- Number of and reasons for unscheduled visits and phone calls

JAEBCENTER FORHEALTH RESEARCH

- Number of participants who stopped treabnent and reasons

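### The 168-hour CGM rule and the 50% closed-loop rule together drop early stoppers from both CGM safety non-inferiority tests, and no sensitivity analysis shows whether that matters

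*Protocol*

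**What the plan says.** Protocol 8.5 sets two conditions for the analyses of CGM and insulin outcomes. The first is that "participants must provide at least 168 hours of CGM data for each of the baseline and trial phase". The second is that they "spend at least 50% of the study period in closed-loop mode". SAP 5.3 repeats both, again asking for the hours "for each of the baseline and trial phase". The two hierarchical safety endpoints, % >250 mg/dL (margin 3 points) and % <54 mg/dL (margin 0.5 points), are CGM outcomes, so both conditions apply to them. Protocol 8.20 and SAP 14 limit all comparisons to available cases. Protocol 8.5 and SAP 5.3 carry sensitivity analyses in their headings but describe none.

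Four other provisions bear on the point:

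- **Events.** Protocol 8.5 also says: "All participants who enroll in the PEDAP-AI study will be included in the safety analyses of endpoints" not measured by CGM. No data minimum applies there.
- **CGM window.** Under Protocol 8.6, "CGM metrics will be calculated from the beginning of study pump" use. SAP 5.4 ends a non-completer's window at the final contact.
- **Adherence metrics.** SAP 8 says: "For participants who do not complete the study these metrics will be prorated". It does not say that this governs the 50% condition in SAP 5.3.
- **Adaptation-period tables.** SAP 6.4 has its own threshold: "Participants must provide CGM data for at least 75% of the" period concerned.

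Protocol 6.6.1 foresees stopping for harm. One ground for discontinuing the device is: "The investigator believes it is unsafe for the participant to continue on the intervention".

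**The concern.** A child taken off the system early because glucose control deteriorated may fail one or both conditions. Whether the child enters the CGM safety tests would then depend on what happened after pump start, which is what the tests are meant to measure. The mean changes in % <54 and % >250 would describe children who tolerated the system long enough to qualify.

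The SAP already accepts partial records from non-completers, so the plan does not object to short follow-up as such. The thresholds defeat that intention for the earliest leavers. With a target of 30 completers and a 0.5-point margin, a few omitted records could matter, and nothing planned would show it.

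**Working it through.** The plan has no power, attrition or variability figure to reproduce; Protocol 8.3 says that the study is not formally powered. The 168 h, 50%, 75%, 56-day, 30-child and margin figures are from the documents. Sensor capture, SDs, number of early stoppers and their changes are assumptions. The plan does not state the sidedness of the non-inferiority tests; the upper limit of a two-sided 95% interval (one-sided 2.5%) is assumed.

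**1. Time needed for 168 h.** Days = 168 / (24 x capture).

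| Capture | 100% | 90% | 80% | 70% |
|---|---|---|---|---|
| Days | 7.0 | 7.8 | 8.75 | 10.0 |

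**2. The 50% condition.** On a fixed 8-week denominator, 0.50 x 56 = 28 days are needed. A child who stops at day 7 has at most 7/56 = 12.5%, and at day 10 at most 10/56 = 17.9%. Every device stopper before about day 28 is out, whatever CGM was recorded. If the denominator is instead prorated to final contact, a child in closed loop for most of a short stay meets 50%, and the 168 h condition decides.

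**3. SAP 6.4.** The first adaptation period lasts 3 days, plus or minus 1. Its 75% threshold is 0.75 x 48, 72 or 96 h = 36, 54 or 72 h. A child who leaves on day 5 at 90% capture has 5 x 24 x 0.9 = 108 h. That can satisfy SAP 6.4 but not SAP 5.3.

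**4. Effect of adding early stoppers back.** Take 30 analysed children with mean change 0 and SD s, and add k children with change X.

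- Mean = kX / (30 + k).
- Variance = [29s² + 30kX²/(30 + k)] / (29 + k).
- Upper limit = mean + t x √(variance / (30 + k)).

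Example for % <54 with s = 0.5, k = 1, X = 5: mean = 5/31 = 0.161. Variance = (7.25 + 24.19)/30 = 1.048. Standard error = √(1.048/31) = 0.184. With t = 2.042 the upper limit is 0.161 + 0.376 = 0.537.

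| % <54, margin 0.5 | Upper limit, s = 0.3 to 1.0 |
|---|---|
| None added | 0.11 to 0.37 |
| One at +2 | 0.24 to 0.45 |
| One at +3 | 0.32 to 0.51 |
| One at +5 | 0.51 to 0.65 |
| Two at +5 | 0.77 to 0.88 |

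| % >250, margin 3 | s = 5 | s = 8 |
|---|---|---|
| None added | 1.87 | 2.99 |
| One at +20 | 2.88 | 3.82 |
| Two at +20 | 3.74 | 4.56 |

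**5. Simulated verdicts for % <54.** The retained children have mean change 0.1 to 0.2 and SD 0.6 to 0.9; a stopper's change averages +5 (SD 2). With two stoppers the expected mean is (30 x 0.1 + 10)/32 = 0.41 to (30 x 0.2 + 10)/32 = 0.50. The share of 20,000 simulated trials declaring non-inferiority was:

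| Analysis | None added | One added | Two added |
|---|---|---|---|
| Paired t-test | 42-94% | 7-22% | 1-3% |
| Robust (trimmed mean, Wilcoxon or Huber) | 39-94% | 25-88% | 12-79% |

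With one stopper at only +2, the t-test declared non-inferiority in about 26-77% of trials.

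**The case against.** A reader might infer that early harm from AI-initiated settings disappears from the safety results. The documents do not support that. Stopping the device because of hypoglycemia or hyperglycemia is itself a reporting criterion (Protocol 6.2.3 and 6.2.4), and so is any adverse event leading to temporary or permanent discontinuation (6.2.2). Protocol 8.4.1, 8.5 and 8.13 tabulate these events for all enrolled children, and 8.15 tabulates treatment stops with reasons. Only the CGM percentages of early stoppers are lost.

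A reader might also infer that the 168 h rule alone removes these children from every CGM analysis. SAP 6.4 has its own threshold, and nothing says whether SAP 5.3 applies on top. The 50% rule may be the binding one, since Protocol 8.14 and SAP 8 speak of an 8-week study period. A child off the device may still reach 168 h by staying in the study. Protocol 6.6.1 speaks both of withdrawing such children and of encouraging them to remain, and those statements must be reconciled.

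The scenario is also narrower than it first appears. Settings can be changed for safety without stopping (Protocol Table 1, 3.2.1, 3.3.4), and those children's data count from pump start. Current pump users may begin on their existing settings (3.2.1), so not every child has AI-initiated settings, although AI adjustment begins at the 3-day visit.

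Finally, the plan switches to robust methods if changes are skewed, and one or two extreme children would produce skewness. The sentence follows the superiority tests in Protocol 8.8 and SAP 6.1, so its reach to non-inferiority is unclear. A robust estimate also departs from the mean difference named in the hypotheses.

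All of this narrows the point. None of it removes the selection from the two CGM tests.

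**Conclusion.** The concern holds in limited form: a cheap improvement. The 168 h and 50% conditions together exclude early stoppers from both CGM non-inferiority tests, exclusion can depend on the harm being tested, and no sensitivity analysis is planned. The 7-to-10-day figure assumes 70-100% capture; the day-28 figure assumes a fixed 8-week denominator.

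The effect on the verdict is an illustration only. One or two excluded children with large changes could alter the % <54 result under a paired t-test; smaller changes or robust methods weaken this considerably. It would be too strong to say that the conclusion would reverse, because the documents give no early-stop rate, SD or expected change. If no child stops early, the results are identical.

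**What to change.** Keep the main analysis as planned, and make three additions to Protocol 8.5 and SAP 5.3.

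1. Add a sensitivity analysis of both non-inferiority tests. Include every child with adequate baseline CGM and any trial-phase CGM after pump start, regardless of the 168 h and 50% conditions. Run it with the paired t-test and with the planned robust method, which should be named. Report whether either verdict changes.
2. List % <54, % >250, hours of CGM and reason for stopping for each child excluded by either condition.
3. Define the denominator of the 50% condition, and state that the SAP 6.4 adaptation-period tables use only that section's 75% threshold.

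The cost is some wording, one extra run on data already uploaded and a short listing. The drawback is that a few days of CGM give a noisy value for a child, which is why this should stay a sensitivity analysis beside the main test.

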90 Baseline values for each CGM metric will be computed from the most recent 28 days of CGM data before91 the Screening visit.

92 During the treatment period, CGM metrics will be calculated from the beginning of study pump useuntil

93 the end of the day before the 8-Week visit date or the end of the 59th day after the date of the Closed Loop

94 Initiation visit- whicheveris earlier. For participants who do not complete the study, the date of the final

95 contact will be used in place of the 8-Weekvisit date.

96 A CGM-measured hypoglycemicevent is defined as 15 consecutive minutes with a sensor glucose value

97 below 54 mg/dL. At least 2 sensor values <54 mg/dL that are 15 or more minutes apart plusno

98 intervening values :::54 mg/dL are required to define an event. The end of the hypoglycemic event is

99 defined as a minimum of 15 consecutive minutes with a sensor glucose concentration ::: 70 mg/dL. At least

100 2 sensor values :::70 mg/dL that are 15 or more minutes apart with no intervening values <70 mg/dL are

- 101 required to define the end of an event.
- 102 A CGM-measured hyperglycernicevent is defined as 90 consecutive minutes with a sensor glucosevalue
- above 300 mg/dL. At least 2 sensor values >300 mg/dL that are 90 or more minutes apart plus no
- 104 intervening values \$300 mg/dL are required to define an event. The end of the hyperglycernicevent is
- 105 defined as a minimum of 15 consecutive minutes with a sensor glucose concentration ::,180 mg/dL. At
- 106 least 2 sensor values::,180 mg/dL that are 15 or more minutes apart with no intervening values >180
- 107 mg/dL are required to define the end of an event.

CalculationofInsulin Metlics 108 5.5

- 109 Insulin metrics for comparisons between baseline and follow-up describe the seven daysprior to the 110 visits.
- Baseline insulin metrics will used at reported from the Diabetes Screening CRF. Insulin metrics will be 111
- calculatedat 8 weeks using Tandem pump data. Insulin pump dataon at least Sof7 days will be required 112
- to calculate insulin metrics. Weight will only be recorded at the Screeningvisit. All calculations of 113
- 114 units/kg will use this weight,

Calc ula tion of CGM and Insulin Metlics for Comparison with the PEDAP 115 5.6 116 Histor ical Conti ol Group

117 Results from this PEDAP-AI study will be compared with those from a sample of participants from the

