prior PEDAP study. For this analysis, participants from the prior PEDAP study will be limited to those 118

- 119 whose RCT baseline HbAlc values are no more than 0.2 percentage points outside of the range observed
- 120 among the PEDAP-AI participants. Basdine metrics for the PEDAP historical control group will be as
- reported for the PEDAP RCT. 121
- The follow-up period for these comparisons will be the7m and gm weeks of study pump use. For PEDAP-122
- 123 AI participa, ntsthis will be the period from the adjustment of pump settings at the 6-Week visit until the
- end of the day before the 8-Week visit. If the 6-Week visit is missed, data from the 14 days before the 8-124
- Week visit will be used. PEDAP-AI participants will be excluded from these analyses if they miss the 8-125
- 126 Week visit. For the PEDAP historical control group, follow-up metrics will be calculated from the 14
- daysprior to the 56m day after the date of the beginning of study pump use. These data will come from the 127
- RCT phase for those who were assigned to the CLC group and Extension phase for those who were 128
- 129 assigned to the SC group. Participantsmust have spent at least SO% of the time between pump initiation and the end of the follow-up period in closed-loopmode, and provided at least 168 hours of data in both
- 130
- the baseline and follow-up periods for inclusion in analyses. 131
- 132 Baseline insulin metrics will usedata reported from the Diabetes Screening CRF. Insulin data must be
- 133 presenton at least 70% of follow-up days to calculate insulin metrics. The day of the 6-Weekvisit will be
- excluded from the calculation of PEDAP-AI participants' insulin metrics. Calculation of units/kg will use 134
- 135 the weight from the Screening visit only.
- 136 5.7 Analysis \Vindows

137 For any analysis or tabulation that involves HbAlc measured at the Closed Loop Initiation visit, the 138 sample must be collected no earlier than three daysprior to the visit and no later than 21 days after the 139 visit.

140 6 Analysis

141 Analysis of the Hiera rchicalEndpoints 6.1

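### Both CGM non-inferiority tests are limited to children with at least 50% closed-loop time, and no analysis without that post-baseline condition is planned

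*Protocol*

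**What the plan says.** Protocol 8.5 sets two conditions for any analysis of CGM or insulin outcomes: 168 hours of CGM data in both the baseline and the trial phase, and that the child "spend at least 50% of the study period in closed-loop mode". SAP 5.3 repeats the rule ("trial phase and spend at least 50% of the study" period in closed loop). Protocol 8.8 and SAP 6.1 open the testing hierarchy with non-inferiority on % >250 mg/dL (limit 3 points) and on % <54 mg/dL (limit 0.5 points), followed by five superiority tests. All seven are CGM outcomes, so the rule governs all of them.

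The wider set covers only endpoints not measured by CGM: "All participants who enroll in the PEDAP-AI study will be included in the safety analyses of endpoints" of that kind. Both sections carry sensitivity analyses in their title, but neither describes one. Protocol 8.20 and SAP 14 add only that comparisons use available cases.

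SAP 5.3 does not say what the 50% is a share of. SAP 8 does define a window for closed-loop use: "System use metrics will be calculated from the beginning of study pump" use to the day before the 8-Week visit or day 59, whichever is earlier. It then adds: "For participants who do not complete the study these metrics will be prorated", with the final contact as the end date. SAP 5.4 treats the CGM window in the same way ("For participants who do not complete the study, the date of the final" contact replaces the visit date). For the PEDAP comparison only, SAP 5.6 writes out its own denominator: at least half "of the time between pump initiation and the end of the follow-up period".

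Protocol 6.6.1 lists reasons for stopping the device, among them "The investigator believes it is unsafe for the participant to continue on the intervention". It says that a child who meets a listed reason is withdrawn from the study. It closes by saying that a child whose device is stopped is encouraged to stay until the final visit.

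**The concern.** Time in closed loop is observed only after the pump is started, and it can reflect how well the child does on the system. A safety comparison restricted on such a variable answers a narrower question: what happened in children who stayed mostly in closed loop. The 168-hour condition already secures a minimum of data, so what the 50% condition adds is the removal of children whose data are otherwise usable.

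The realistic exclusions are children who hardly use closed loop, and children who stop the device early and stay in follow-up. At stake is whether the two CGM safety conclusions also hold with those children included. The planned tables of closed-loop use and of reasons for stopping, and the participant flowchart (Protocol 8.14 and 8.15, SAP 8 and 9), would show how many children are affected. They would not show whether the non-inferiority results survive.

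**Working it through.** The plan gives no power figure, SD of change or expected exclusion rate; Protocol 8.3 says that the study is not formally powered. There is therefore nothing to reproduce, and the SDs, means and counts in step 3 are assumptions.

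**1. Who falls below 50%.** Half of 56 days is 28 days, or 28 × 24 = 672 hours, which equals 672 / 4 = 168 pauses of four hours each. Short pauses, such as the four hours after syringe insulin (Protocol 3.2.3 and 4.3.4), will rarely exclude anyone.

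**2. One child, two classifications.** Take a child in full closed loop until the device is stopped at day 20.
- Followed to week 8: 20/56 = 36% (20/59 = 34% at the latest cut-off). Excluded, despite up to 20 × 24 = 480 hours of on-device CGM, well above 168.
- Withdrawn at day 20 and prorated under SAP 8: 20/20 = 100%. Included.

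The device experience is identical. Which row applies depends on which of the two sentences in Protocol 6.6.1 governs.

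**3. How much the excluded children would have to worsen.**
Inputs: margins 3 and 0.5 points (Protocol 8.2 and 8.8). Assumed: n = 30 included children with mean change m and SD s, and k = 3 excluded children who all change by d. Protocol 8.8 does not state the sidedness of the non-inferiority tests, so both one-sided 0.025 and 0.05 are shown.

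With N = n + k = 33:
- mean = (30m + 3d) / 33
- SS = 29s² + (30 × 3 / 33)(d − m)²
- upper limit = mean + t(1 − α, 32) × √(SS / 32 / 33)

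Set the upper limit equal to the margin and solve for d.

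Check for >250 mg/dL with m = 0, s = 5, d = 10.76, α = 0.025: mean = 32.28 / 33 = 0.978; SS = 725 + 2.727 × 115.8 = 1040.8; standard error = √(1040.8 / 32 / 33) = 0.993; upper limit = 0.978 + 2.037 × 0.993 = 3.00.

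| Endpoint (margin) | SD | Included mean | d at 0.025 | d at 0.05 |
|---|---|---|---|---|
| >250 (3) | 5 | 0 | 10.8 | 13.2 |
| >250 (3) | 5 | +0.5 | 7.7 | 10.1 |
| >250 (3) | 5 | +1.0 | 4.1 | 6.7 |
| >250 (3) | 4 | 0 | 12.5 | 14.5 |
| >250 (3) | 6 | 0 | 8.6 | 11.5 |
| <54 (0.5) | 0.6 | 0 | 2.2 | 2.5 |
| <54 (0.5) | 0.6 | +0.1 | 1.7 | 2.0 |
| <54 (0.5) | 0.6 | +0.2 | 1.1 | 1.4 |
| <54 (0.5) | 0.4 | 0 | 2.4 | 2.7 |
| <54 (0.5) | 1.0 | 0 | 1.4 | 1.9 |

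Same formula with d = +10 on >250 mg/dL and SD 5: the upper limit is 2.89 (0.05: 2.56) at included mean 0, so non-inferiority holds. It is 3.32 (2.99) at +0.5 and reverses only at 0.025. It is 3.75 (3.42) at +1.0 and reverses at both levels.

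If the robust methods that Protocol 8.8 keeps for skewed changes were used here, these figures would change.

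**The case against.** **The restricted set is a defensible choice.** It addresses safety while the system is in use. Adding off-system time may pull the change toward zero, which favours non-inferiority, so the wider set is not clearly the stricter test. This stands. It is a reason to report both sets, not a reason to report only one.

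**Safety is covered elsewhere.** Severe hypoglycemia, DKA and the other non-CGM safety endpoints are analysed in every enrolled child. This stands, and the point is confined to the CGM tests. A reader might infer that the whole safety assessment rests on a selected group; the documents do not support that.

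**Children stopped for safety may not be dropped at all.** A reader might infer that the rule systematically removes the children who do worst. Protocol 6.6.1 does not support that as it stands: one of its sentences withdraws such a child, and SAP 8 proration could then keep the child in at 100%. Its other sentence allows the opposite result. What stands is that membership is unsettled for these children.

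**The denominator is clear enough.** SAP 8 uses nearly the same term for its window, and no passage states a fixed 8-week denominator. This stands: it is a missing cross-reference, not a contradiction.

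**It is a small pilot, and reversal needs large worsening.** This stands for results well inside the margin. The plan nevertheless sets margins, formal tests and type 1 error control, so the robustness of those tests is a fair question.

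**Conclusion.** The point holds for the two CGM non-inferiority tests and the superiority tests behind them: they condition on post-baseline closed-loop use, and no planned analysis shows the result without that condition. It should be fixed, as a gap in robustness and not as a demonstrated bias. The documents give neither the size nor the direction of any bias, and it is zero if no child falls below 50%.

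Under the assumptions in step 3 (30 included, 3 excluded, SD 5 or 0.6, included mean 0, one-sided 0.025), reversal takes a worsening of about 10.8 points on >250 mg/dL or 2.2 points on <54 mg/dL in each excluded child. At an included mean of +1.0 or +0.2 this falls to 4.1 or 1.1 points. The exclusion therefore matters mainly when the included result is already near the margin.

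A reader might also infer that pauses for illness or after syringe insulin would drop children. The arithmetic in step 1 shows that short pauses alone will rarely do so.

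**What to change.** Keep the current analysis set and the testing hierarchy. In SAP 5.3, and in Protocol 8.5 at its next amendment:

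1. Add a sensitivity analysis, outside the hierarchy, of at least both non-inferiority comparisons in every child who starts the study pump and has at least 168 hours of CGM data in each phase, whatever the closed-loop use. Report it beside the ≥50% set and state whether the conclusions differ.
2. List the children excluded by the 50% rule, with the reason and their available CGM values.
3. As an editorial addition, let the 50% rule cite the SAP 8 window and its proration.

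Separately, the two sentences in Protocol 6.6.1 on withdrawal and on staying in the study must be reconciled, because they decide how an early stopper is classified.

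The analysis cost is one extra run and one listing, from data already collected. The protocol wording needs IRB approval (Protocol 10.2), so it can wait for the next amendment. The downsides are that off-system time may make the added estimate noisier or pull it toward no difference, so the two sets must be read together, and that children with under 168 hours of CGM data in either phase are still left out.
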